10.4.2 Echocardiogram

Number and percentages of patients with respect to echocardiogram qualitative assessments results (normal / other) regarding Aortic, Mitral, Tricuspid, and Pulmonic will be presented in a shift table from baseline to Week 52 and Week 104 by treatment group.

LVM calculated by echocardiogram will only be listed.

For some patients, echocardiogram at Week 104 was postpone due to COVID-19 and eventually performed as part of the extension study, so the data will not be analyzed as part of this study (Section 6).

10.5 Short Form Brief Pain Inventory (BPI)

Descriptive statistics of the qualitative assessments and change from baseline regarding pain severity (worst pain in the last 24 hours, least pain in the last 24 hours, right now and average) and pain interference will be summarized at each visit by treatment group. For each of the pain

severities and pain interferences assessments, a 95% CI based on the t-distribution for a paired sample, for the change from baseline, will be presented. A 95% CI of the change from Baseline to 12 months and to 24 months between the two treatment groups will be done using t-distribution for two samples.

The analysis for the average pain over the last 24 hours will also be done for the following subgroups: ADA status, gender and FD classification.

The proportion of patients whose average pain severity did not change or improved compared to baseline (the difference from baseline is ≤ 0) and the proportion of patients whose average pain severity deteriorated compared to baseline (the difference from baseline > 0) will be summarized at each visit by treatment group. If the BPI assessment was postponed due to COVID-19, the analysis will use the data collected on site at the first time a patient could attend an on-site visit.

10.6 Urine Protein/Creatinine Ratio

Urine protein/creatinine ratio (UPCR), by a spot urine test, will be summarized at each visit by treatment group using the following three categories:

- UPCR ≤ 0.5 gr/gr,
- 0.5 < UPCR < 1gr/gr
- $1 \le UPCR gr/gr$

The laboratory limit of detection for urine protein is 4 mg/dL, and for a large number of the measurements, the protein is undetectable ('<4 mg/dL'), resulting in a UPCR of '< x gr/gr' (where x is calculated by 4 divided by the measured level of creatine and the '<'comes from the protein value). Any such observation will be classified in one of the above categories, ignoring the '<' sign in the observation. This is considered a conservative assignment to categories.

The analysis will be repeated for the following sub-groups: ADA status, gender, use of ACEi/ARB and FD classification.

The shift from baseline to Week 52 (or early termination) and to Week 104 (or early termination), between UPCR categories, will be presented by treatment group. The tables will show the number and percentage of patients in each cell.

The UPCR listing will include the actual observation (i.e., '<' sign will not be removed) as well as the assigned category.

10.7 Stress Test

Qualitative evaluation (yes/no) of symptoms (chest pain, shortness of breath, dizziness, palpitations, and other) and the overall impression: normal stress test (yes/no) will be summarized by count and percentage at each visit by treatment group.

In addition, for overall impression only, a shift from baseline will be presented: normal stress test (yes / no). For patients who terminated early, the table will show their shift to their last assessment prior to discontinuation.

Stress test data ay Week 104 may be missing for a few patients due to COVID-19 (Section 6).

10.8 Mainz Severity Score Index (MSSI)

Descriptive statistics of the total scores and change from baseline of each of the domains (general, neurological, cardiovascular, renal dysfunction, and overall score (sum of these four scores)) will be summarized at each visit the MSSI is evaluated by treatment group. A 95% CI, based on a t-distribution for a paired sample, for the change from baseline, within each treatment arm, will be presented. A 95% CI based on a t-distribution for two samples in the change from baseline to Week 52 and to Week 104 will be presented.

A total MSSI score < 20 is considered as mild; a score $20 \le$ and ≤ 40 is considered moderate and > 40 is considered severe (Beck (2006)). A shift table from baseline to week 52 and to week 104 between the three categories will be presented by treatment arm. For patients who discontinue early, their value at their last assessment will be used for the MSSI analyses.

If a patient missed Week 52 or Week 104 due to COVID-19, his MSSI assessment will be performed at the first time the patient could attend an on-site visit after Week 52 or Week 104.

10.9 Quality of Life (EQ-5D-5L)

Descriptive statistics of the qualitative assessments regarding mobility, self-care, usual activities, pain/discomfort, and anxiety/depression will be summarized at each visit by treatment group. The number and proportion of patients with no change or improvement (difference from baseline is \geq 0) and the number and proportion of patients with a worse score (difference from baseline is \leq 0) will be summarized by visit.

The overall health score (from 0 to 100) will be summarized by treatment group using descriptive statistics at each visit together with the change from baseline. A statistical comparison in the change from baseline to Week 52 and to Week 104 between the two treatment groups will be made using a t-distribution for two-samples.

If a patient missed Week 52 or Week 104 due to COVID-19, their EQ-5D-5L assessment will be performed at the first time the patient could attend a site visit after Week 52 or Week 104.

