14.9 Appendix 9. EQ-5D-5L

Figure 1: EQ-5D-5L (UK English sample version)

Under each heading, please tick the **ONE** box that best describes your health **TODAY**

MOBILITY

- I have no problems in walking about
- I have slight problems in walking about
- I have moderate problems in walking about
- I have severe problems in walking about
- I am unable to walk about

SELF-CARE

- I have no problems washing or dressing myself
- I have slight problems washing or dressing myself
- I have moderate problems washing or dressing myself
- I have severe problems washing or dressing myself
- I am unable to wash or dress myself

USUAL ACTIVITIES (e.g. work, study, housework, family or leisure activities)

- I have no problems doing my usual activities
- I have slight problems doing my usual activities
- I have moderate problems doing my usual activities
- I have severe problems doing my usual activities
- I am unable to do my usual activities

PAIN / DISCOMFORT

- I have no pain or discomfort
- I have slight pain or discomfort
- I have moderate pain or discomfort
- I have severe pain or discomfort
- I have extreme pain or discomfort

[figure not shown]
ANXIETY / DEPRESSION

- I am not anxious or depressed
- I am slightly anxious or depressed
- I am moderately anxious or depressed
- I am severely anxious or depressed
- I am extremely anxious or depressed

- We would like to know how good or bad your health is **TODAY**.
- This scale is numbered from **0** to **100**.
- **100** means the best health you can imagine.
0 means the worst health you can imagine.
- Mark an **X** on the scale to indicate how your health is **TODAY**.
- Now, please write the number you marked on the scale in the box below.

YOUR HEALTH TODAY =

The best health
you can imagine

The worst health
you can imagine

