14.2.4.1.2	Summary of Plasma Gb3 Concentrations by ADA Status	ITT
14.2.5.1	Summary of Urine Lyso-Gb3 Concentrations	ITT
14.2.5.1.1	Summary of Urine Lyso-Gb3 Concentrations by Gender	ITT
14.2.5.1.2	Summary of Urine Lyso-Gb3 Concentrations by ADA Status	ITT
14.2.6.1	Summary of Cardiac MRI by Hypertrophy Status	ITT
14.2.6.1.1	Summary of Cardiac MRI by Gender and by Hypertrophy Status	ITT
142612	Summary of Cardiac MRI by FD Classification and by	ITT
14.2.6.1.2	Hypertrophy Status	ITT
14.2.6.2	Cardiac MRI - Shift in LVMI Fibrosis Segments	ITT
14.2.6.3	Cardiac MRI – Shift in Hypertrophy Status	ITT
14.2.7	Echocardiogram Qualitative Assessments – Shift from Baseline	ITT
14.2.8.1	Summary of Short Form Brief Pain Inventory - Severity Domains	ITT
142011	Summary of Short Form Brief Pain Inventory - Average Pain	ITT
14.2.8.1.1	Over 24 Hours by Gender	ITT
14.2.8.1.2	Summary of Short Form Brief Pain Inventory - Average Pain	ITT
14.2.0.1.2	Over 24 Hours by ADA Status	111

Г		T
14.2.8.1.3	Summary of Short Form Brief Pain Inventory - Average Pain Over 24 Hours by FD Classification	ITT
14.2.8.2	Short Form Brief Pain Inventory - Proportion of Patients with Improvement or No Change in Average Pain Severity	ITT
14.2.8.3	Summary of Short Form Brief Pain Inventory - Interference Domains	ІТТ
14.2.9.1	Frequency of UPCR Categories	ITT
14.2.9.1.1	Frequency of UPCR Categories by Gender	ITT
14.2.9.1.2	Frequency of UPCR Categories by ADA Status	ITT
14.2.9.1.3	Frequency of UPCR Categories by FD Classification	ITT
14.2.9.1.4	Frequency of UPCR Categories by Usage of ACEi or ARB	ITT
14.2.9.2	UPCR Categories - Shift from Baseline to Week 52 and to Week 104	ITT
14.2.10.1.1	Summary of Stress Test Qualitative Assessments – Overall Impression	ITT
14.2.10.1.2	Summary of Stress Test Qualitative Assessments – Symptoms	ITT
14.2.10.2	Stress Test Overall Impression - Shift from Baseline	ITT
14.2.11.1	Summary of Mainz Severity Score Index (MSSI)	ITT
14.2.11.2	Mainz Severity Score Index (MSSI) Overall Score - Shift from Baseline	ITT
14.2.12.1	Summary of Quality-of-Life EQ-5D-5L Overall Health Score	ITT
14.2.12.2	Frequency of Quality-of-Life EQ-5D-5L Qualitative Assessments	ITT
14.2.12.3	Proportion of Patients with Improvement or No Change of Quality-of-Life EQ-5D-5L Qualitative Assessments	ITT
14.2.13.1	Proportion of Patients Used Pain Medications	ITT
14.2.13.2	Number of Different Pain Medications Used by Patients During the Study	ІТТ

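### The EQ-5D-5L item rule in SAP 10.9 suits a higher-is-better scale, but the items are listed from best to worst and no coding is stated

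*SAP*

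**What the plan says.** SAP 10.9 first announces "Descriptive statistics of the qualitative assessments regarding mobility, self-care, usual activities, pain/discomfort, and anxiety/depression", summarised by visit and arm. It then splits patients into two groups by their difference from baseline:

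- The favourable group is introduced by "The number and proportion of patients with no change or improvement (difference from baseline is", followed by an inequality of zero or more.
- The unfavourable group is described as "patients with a worse score (difference from baseline is", followed by an inequality that appears in our text as zero or less.

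The list of tables in SAP 14.1 shows where the rule is used. Table 14.2.12.3, on the ITT set, is titled "Proportion of Patients with Improvement or No Change of Quality-of-Life EQ-5D-5L Qualitative Assessments". The 0-100 overall health score has its own paragraph in 10.9 and its own table, 14.2.12.1.

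Protocol Appendix 9 shows the instrument. Each item has five tick boxes without numbers, running from best to worst. Mobility, for example, starts with "I have no problems in walking about" and ends with being unable to walk about. On the 0-100 scale, by contrast, 100 is the best health imaginable.

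SAP 10.5 has a rule of the same kind for BPI. It takes patients "whose average pain severity did not change or improved compared to baseline (the difference from baseline is" zero or less as the favourable group, and a difference above zero as deterioration. Protocol Appendix 7 anchors the BPI severity items at 0 for no pain and 10 for the worst imaginable.

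**The concern.** The BPI severity scale and the EQ-5D-5L items are both presented from best to worst, yet the SAP gives them opposite inequalities and does not explain why. The inequality in 10.9 would be right for the 0-100 score, but it is attached to the five items.

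A programmer who numbers the boxes in printed order and follows 10.9 literally would produce a table with the labels reversed. Each percentage would lie in a plausible range, so the table would not look wrong on its face. EQ-5D-5L is a listed secondary endpoint, SAP section 1 makes the SAP govern over the protocol, and SAP 16.3.1 has the blinded team program from the updated SAP. The printed rule is therefore the one likely to be coded.

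**Working it through.** The plan states no figure to reproduce. The check applies the printed rule to every possible change on one item.

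**Inputs**

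- Five levels per item, listed from best to worst (Protocol Appendix 9).
- Favourable group: difference of zero or more (SAP 10.9).
- Assumption A, not in the documents: levels are numbered 1 (no problems) to 5 (unable or extreme), in listed order.
- Assumption B, not stated for EQ-5D-5L: difference d = visit level minus baseline level. The BPI rule in SAP 10.5 fits this sign convention.
- For this step the worse group is taken as d < 0, the reading that leaves zero in one group only.

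**Enumeration.** There are 5 × 5 = 25 pairs of baseline and visit level: 5 unchanged, 10 with a higher visit level and 10 with a lower one.

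| True change | Pairs | 10.9 rule, levels as listed | 10.9 rule, levels reversed | BPI-type rule, levels as listed |
|---|---|---|---|---|
| Improved | 10 | d < 0: worse | d > 0: favourable | d < 0: favourable |
| Unchanged | 5 | d = 0: favourable | d = 0: favourable | d = 0: favourable |
| Worsened | 10 | d > 0: favourable | d < 0: worse | d > 0: worse |

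With levels as listed, the favourable group holds 5 + 10 = 15 pairs, and the 10 are all worsenings. The worse group holds the 10 improvements. With the BPI-type rule the favourable group holds 5 + 10 = 15 pairs, the 10 now being improvements; the worse group holds the 10 worsenings, and no pair is in both. With reversed coding the printed direction is right.

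**Effect on the reported proportions.** Let u, w and i be the true shares unchanged, worsened and improved on one item, with u + w + i = 1.

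- Favourable as reported: u + w = 1 − i. Correct value: u + i = 1 − w.
- Worse as reported: i. Correct value: w.
- Error in the favourable proportion: (1 − i) − (1 − w) = w − i.

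The documents give no shares, so these are assumed for illustration:

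| u / w / i | Favourable, reported | Favourable, correct | Worse, reported | Worse, correct |
|---|---|---|---|---|
| 40 / 35 / 25% | 75% | 65% | 25% | 35% |
| 60 / 25 / 15% | 85% | 75% | 15% | 25% |
| 80 / 15 / 5% | 95% | 85% | 5% | 15% |

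The error is 10 points in each row only because w − i was set to 10 points each time.

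**Between arms.** Suppose one arm has 60 / 15 / 25% and the other 60 / 25 / 15%. The correct favourable proportions are 60 + 25 = 85% and 60 + 15 = 75%. The reported ones would be 60 + 15 = 75% and 60 + 25 = 85%. The arm that did better would be shown as doing worse.

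**The case against.** **The direction depends on coding that we cannot see.** Appendix 9 is a tick-box form without numbers, and neither document defines the difference for these items. The eCRF codes and table shells are not in the documents. If levels are stored with higher as better, or the difference is baseline minus visit, the printed direction is correct. This stands, and it is why the misclassification is stated as conditional. It does not remove the point: a rule based on the sign of a difference cannot be applied reliably until the coding is given, and the only comparable rule in the SAP has the opposite sign.

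**A reader might also infer that zero change is counted twice.** As the text reached us, the two inequalities are zero or more and zero or less. Unchanged patients would then be in both groups under any coding, and with 40% to 80% unchanged the two proportions would sum to 140% to 180%. The documents do not support calling this an error in the plan. SAP 9.3.1 appears with the UPCR stratum as at most 1 versus at least 1, whereas SAP 3, 3.2 and 17.5 have it as below 1 versus at least 1, so a strict sign may have been lost in reading the PDF. The verbal labels also put no change in the favourable group only. The sign should be checked; no overlap is claimed.

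**The intent is clear and other outputs would expose an inversion.** Table 14.2.12.2 gives the frequency of each response, listing 16.2.2.8 gives individual data, and SAP 16.3.1 plans a dry run. An attentive reader could catch the contradiction there. This lowers the risk but depends on someone comparing the tables.

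**The impact is small.** This is accepted. SAP 7.6.2 makes no significance claims for endpoints other than the primary, and the only planned between-arm comparison for EQ-5D-5L is on the 0-100 score.

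**Conclusion.** The point holds in conditional form. The inequality in SAP 10.9 fits a higher-is-better scale, while the items it governs are listed from best to worst and the SAP's BPI rule runs the other way. If levels are numbered as listed and the difference is visit minus baseline, every patient whose level changes on an item is put in the wrong group for that item: 10 of 10 possible worsenings and 10 of 10 possible improvements. Under reversed coding, or a difference taken as baseline minus visit with levels as listed, the direction is right and only the missing definition remains.

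It would go too far to say that the EQ-5D-5L endpoint as a whole is reversed. The rule feeds one descriptive table, with no test or interval attached. The item frequencies, the 0-100 score analysis and the primary eGFR analysis do not use it. The point is worth correcting because the table could otherwise mislead on a secondary endpoint and the correction is almost free.

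**What to change.** In SAP 10.9:

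1. State that the five items are coded 1 (no problems) to 5 (unable or extreme).
2. Define the difference as visit minus baseline.
3. Set a difference of zero or less as no change or improvement, and a difference above zero as worse, as SAP 10.5 does for BPI.
4. Leave the 0-100 score, where higher is better, as it is.

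Confirm the item codes in the eCRF before programming, and recode first if they run the other way. Check the second inequality in 10.9 against the source PDF.

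The cost is one line of SAP text and the matching line in the program for Table 14.2.12.3. No data collection or other analysis changes.

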10.10 Pain Medication

Prior and concomitant medications reported during the study will be coded by World Health Organization (WHO) Drug Dictionary 20160601E. Pain medication will be identified based on the classification assigned by the investigator in the eCRF. Pain medications will be summarized by the count and percentage of the patients with each medication by standardized medication name within medication class. Medication classes will be presented alphabetically; within each medication class, standardized medication names will be sorted by decreasing order of PRX-102 frequency.

The number of patients who used pain medication at any time during the study will be summarized by treatment group presenting count and percentage of patients by the number of medications they used (0, 1, 2, up to the maximum, where medications with identical standard names are counted once and 0 represents patients who did not take any pain medication during the study).

The change from baseline to the last visit (scheduled or unscheduled) in the number of different pain medications used will be examined by shift tables with the following categories for the number of pain medications used: 0, 1, and 2+. The tables will be presented by treatment arm. For patients who terminated early, the table will show their shift to their last assessment prior to discontinuation. This analysis will be based on the pain medication used on the day of the baseline visit, and the day of last visit.

Section 7.2.1 provides information on handling partial or complete missing dates of pain medications.

10.11 Fabry Clinical Events

Following Hopkin (2016), Fabry clinical events (FCE) are classified into four categories: renal, cardiac, cerebrovascular and death due to non-cardiac reasons. The adjudicated decisions will be made by the Sponsor Medical Monitor in a blinded fashion, based on reported adverse events and clinical information included in the data base. The criteria for FCE are the following:

- 1. Renal events;
 - a. The first occurrence of either initiation or chronic dialysis (>40 days)
 - b. Renal transplantation
- 2. Cardiac events;
 - a. Cardiac related death
 - b. Myocardial infarction
 - c. First time congestive heart failure
 - d. Atrial fibrillation
 - e. Ventricular tachycardia
 - f. Evidence of progressive heart disease severe enough to require a pacemaker
 - g. Implantation of pacemaker
 - h. Bypass surgery
 - i. Coronary artery dilatation
 - i. Implantation of defibrillator
- 3. Cerebrovascular events;
 - a. Hemorrhagic or ischemic stroke
 - b. Transient Ischemic Attack
- 4. Death non-cardiac-related

The number and percentage of patients with at least one FCE overall and for each of its components will be presented by treatment arm together with the number of events as well rate adjusted to 100 person-years defined as number of events X 100 / total exposure (in years). For the number of patients with at least one FCE, patients who had more than one type will be counted only once.

Time to 1st event will be presented graphically by Kaplan-Meier by treatment group. The time (months) will be measured from date 1st infusion and patients with no FCE will be censored at the date of last infusion. The number of days will be converted to months by multiplying by 12/365.25.

The FCE listing will show the categories by Hopkin as well as by SOC and PT and the time to the event from randomization (months).

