6.2.4 Removal of Subjects from Therapy or Assessment

Reasons for permanent discontinuation include the following:

- The subject experiences two or more Grade 3 toxicities or one or more Grade 4 toxicity considered by the investigator associated with PRX-102 or agalsidase beta treatment (CTCAE v. 4.03, 2010)
- The subject experiences progressive hypersensitivity or severe hypersensitivity that is not allayed with pre-treatment
- The subject requests to discontinue treatment
- The Investigator feels that it is not in the best interest of the subject to continue treatment and/or if the investigator believes that the subject can no longer be compliant with the requirements of the study

For any discontinuation, the Investigator will obtain all the required details and document the date and the main reason for the premature termination. If the reason for discontinuation is an adverse event, the specific event or the main laboratory abnormality will be recorded in the eCRF. The Investigator will make thorough efforts to document the outcome. The Investigator will attempt to continue to follow the subject for the full duration of the study or at least for 90

days following discontinuation. If circumstances prevent the subject from completing all visits, every attempt will be made to complete all procedures listed in Section 9 for Visit 53.

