8.3.2 Adverse Events

8.3.2.1 Adverse Events (AE) and Serious Adverse Events (SAE)

An adverse event (AE) is any untoward medical occurrence in a subject participating in a clinical trial. An adverse event can be any unfavorable and unintended sign, symptom or disease temporally associated with the use of the study medication, whether or not considered related to the study medication. AEs will be collected from the start of treatment until 90 days following the final visit dose. Any events occurring prior to treatment will be recorded on the medical history page with the event name and onset date and end date if not continuing. Pre-existing, known clinically significant conditions observed at screening should be recorded as medical history.

This definition also includes accidental injuries, reasons for any change in medication (drug and/or dose) other than planned titration, reasons for admission to a hospital, or reasons for surgical procedures (unless for minor elective surgery for a pre-existing condition). It also includes adverse events commonly observed and adverse events anticipated based on the pharmacological effect of the study medication. Any laboratory abnormality assessed as clinically significant by the Investigator must be recorded as an adverse event.

A treatment emergent adverse event is any adverse event occurring after start of study medication and within the time of residual drug effect (90 days after the last administration of the study medication), or a pre-treatment adverse event or pre-existing medical condition that worsens in intensity after start of study medication and within the time of residual drug effect.

Adverse events should be recorded as diagnoses, if available. If not, separate sign(s) and symptom(s) are recorded. One diagnosis/symptom should be entered per record. Treatment-related hypersensitivity/infusion reactions are defined in Appendix 3 and can be defined as a single AE at the Investigator's discretion.

Note that death is not an event, but the cause of death is. An exception is the event of sudden death of unknown cause. Note that hospitalization is not an event; however, the reason for hospitalization is. Procedures are not events; the reasons for conducting the procedures are. In general, only the reason for conducting the procedure will be captured as an adverse event. However, if deemed necessary by the Investigator, a procedure can be captured along with the reason for conducting the procedure.

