11.1 Exposure

Duration of exposure to study drug (months) is based on the number of days a patient received drug and is defined as

(Last day of study drug – the first day of study drug + 1)*12/365.25.

Duration of exposure (months) will be summarized using descriptive statistics by treatment arm. The analysis will be repeated for all subgroups defined in Section 7.4.

The cumulative exposure (over all patients within treatment arm) in person-months will be provided.

The number of partial or complete infusions that a patient received will be summarized by treatment arm and by location of administration (home/site). Summary of infusion duration (hours) by visit will be presented by treatment arm.

Listing of infusion should include whether the complete dose was administered or not.

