- 15. At the interim analysis, IRR were considered to occur within 2 hours. For the final analysis two-time frames of IRR are considered: within 2 hours and within 24 hours.
- 16. Following analysis that was done as part of the Summary of Clinical Safety (2.7.4) for the MAA, an analysis of infusion premedication and IRR-2H was added.
- 17. In light of the 2:1 randomization ratio, adjustment to the exposure is added when presenting number of TEAE, number of IRR and number of FCE.
- 18. Adding a shift table for ADA: from baseline to visit 53.
- 19. Since randomization often occurred about two weeks prior to 1st infusion, Kaplan-Meier curves are updated to measure time from date of 1st infusion instead of randomization. In case of no events, time should be censored at the time of last infusion.

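### SAP 10.11 lets Fabry clinical events after the last infusion count, but ends person-time and event-free follow-up at the last infusion, so the rate and Kaplan-Meier curve lean slightly upward

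*SAP*

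**What the plan says.** SAP 10.11 has FCEs adjudicated "based on reported adverse events and clinical information included in the data base". It gives no end date for a qualifying event and no on-treatment restriction. Three rules then use the date of the last dose:

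- **Kaplan-Meier curve (SAP 10.11).** Time runs from first infusion, and "patients with no FCE will be censored at the date of last infusion". SAP 13.2, item 19, has the same rule: "In case of no events, time should be censored at the time of last infusion". Both apply only to patients without an event.
- **Rate (SAP 10.11).** It is "rate adjusted to 100 person-years defined as number of events X 100 / total exposure (in years".
- **Exposure (SAP 11.1).** "Duration of exposure to study drug (months) is based on the number of days a patient received drug", computed as "Last day of study drug – the first day of study drug + 1)*12/365.25". Off-drug time is not included.

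Data collection goes on after the last dose. Protocol 8.3.2.1 states that "AEs will be collected from the start of treatment until 90 days following the final visit dose". For patients who stop early, Protocol 6.2.4 asks the investigator to "attempt to continue to follow the subject for the full duration of the study", or for at least 90 days. The SAP 11.2 definition of a treatment-emergent event also has no end limit. No section excludes an FCE after the last infusion or adds off-drug time to the denominator.

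**The concern.** Between the last infusion and the end of observation, a patient stays in the Kaplan-Meier risk set only if an FCE is going to occur. Censoring then depends on the future outcome, which the estimator does not allow. The rate has the matching fault: its numerator covers a longer period than its denominator.

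Events after the last infusion are not a curiosity here. Dosing is every two weeks, so an event that ends treatment falls after the last infusion, and so does nearly every death. Deaths, cardiac and non-cardiac, are FCE components.

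At stake is the comparison between arms. SAP 13.2, item 17, adds exposure adjustment because of the 2:1 randomization. Mismatched windows work against that purpose if stopping differs between arms.

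**Working it through.** **Inputs from the documents.** 78 randomized, planned 52 and 26 (Protocol 10.1). Six discontinued (SAP 16.2): 6/78 = 7.69%, which reproduces the stated 7.7%. AE collection runs to 90 days after the last dose: 90/365.25 = 0.246 years. Treatment lasts 104 weeks: 728/365.25 = 1.993 years, or 729 days = 1.996 years with the +1 in SAP 11.1. The documents give no FCE rate, no stopping times and no split of the six by arm, so those are assumed below.

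**Rate.** With a constant event rate, inflation = (exposure + off-drug time in which an event can count) / exposure.

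1. *Six stop halfway, 90-day capture.* Exposure = (72 + 6 × 0.5) × 1.993 = 149.5 person-years. Off-drug time = 6 × 0.246 = 1.48. Ratio 1.010.
2. *Six stop at month 3, 90-day capture.* Exposure = 72 × 1.996 + 6 × 0.25 = 145.2. 1.48/145.2 = 1.0%.
3. *As 2, all six in the 26-patient arm.* Exposure = 20 × 1.996 + 1.5 = 41.4. 1.48/41.4 = 3.6%.
4. *Six stop, events captured to week 104.* Stopping at 75%, 50% or 25% of the period gives 1.020, 1.040 or 1.061. If all six stop halfway in the 26-patient arm: 3 × 1.993 / (23 × 1.993) = 13.0%.
5. *Planned 15% dropout (12 of 78).* About 1.02 with 90-day capture; 1.04 to 1.13 with capture to week 104.
6. *Completers.* If the first PB-102-F60 infusion comes 14 days after the last study infusion (assumed), the gap is 14/729 = 1.9% of a completer's exposure. For 72 completers that is 72 × 14/365.25 = 2.76 person-years, or 1.8% of 149.5. If nobody rolled over and all 78 had 90 further days: 78 × 0.246 / 149.5 = 12.9%, an upper bound.

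**Kaplan-Meier at 24 months.** Simulation of 400,000 patients; stopping times uniform over 104 weeks; hazard 10 per 100 person-years on and off drug. The true value is 1 − exp(−0.10 × 1.993) = 18.07%.

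| Stopping | Capture | SAP rule | Censored at end of follow-up |
|---|---|---|---|
| 7.7% | 90 days | 18.20% | 18.05% |
| 7.7% | to week 104 | 18.65% | 18.03% |
| 15% | to week 104 | 19.20% | 17.95% |

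The SAP rule lies above the matched rule in these rows, and also in the runs with a hazard of 3 per 100 person-years or a tripled off-drug hazard.

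**Kaplan-Meier at the scale of one arm (26 patients).**

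- *Mid-curve.* Three patients stop at months 6, 12 and 18, and the second has an FCE at month 14. The SAP rule gives 1/25 = 4.0%. Censoring at end of follow-up gives 4.0% with 90-day follow-up and 1/26 = 3.8% with follow-up to month 24.
- *Tail.* One FCE at month 26, the other 25 censored at month 23.9. Under the SAP rule one patient is at risk, so cumulative incidence goes to 1/1 = 100%. If the others are followed to month 26.9, it is 1/26 = 3.8%.

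**The case against.** The strongest reply is that SAP 10.11 nowhere says that an FCE after the last infusion counts. Censoring at last infusion with an on-drug denominator also fits an on-treatment analysis whose event cut-off was left unwritten. This stands in part: the reading rests on the missing cut-off and on a censoring rule confined to event-free patients. But a programmer following the text would include such events. An on-treatment analysis would also need a rule for deaths, which would otherwise almost never qualify.

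The second reply is size, and it largely stands. The rate pools person-time within an arm, discontinuation was low, and many completers may have moved to the extension within weeks. SAP 10.11 plans no test, and SAP 7.6.2 rules out significance claims for endpoints other than the primary.

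A reader might go further in three ways that the documents do not support:

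- *A distortion of about 12% in general.* 90/729 = 12.3% applies only to a completer who does not roll over, and the documents do not say how many there were. Likewise, a ratio such as (0.25 + 0.246)/0.25 = 1.99 for a patient stopping at month 3 describes one patient, not an arm's rate.
- *Late events in stoppers are lost.* Protocol 8.3.2.2 asks for all adverse events during the study, and SAP 10.11 also draws on other clinical information in the database. Any such loss would lower the rate, not raise it.
- *The protocol's collection period should change.* SAP 16.2 puts the last patient's last visit in October 2021, so a change could not recover data.

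**Conclusion.** The point holds as a minor one. Applied as written, SAP 10.11 gives events a longer window than person-time and event-free follow-up, and both the rate and the curve are biased upward. Stoppers' off-drug time adds about 1% to the pooled rate at 6 of 78 with 90-day capture, or about 3.6% in the worst placement considered under that capture. The bias becomes clearly larger, up to about 13% in the cases worked, only if events are captured to week 104 or many completers do not roll over.

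The more practical weakness is the tail of the FCE curve (Figure 15.2.3), where a single late event can produce a meaningless 100%.

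These sizes rest on assumed stopping times, a constant event rate for the ratios, and an unknown arm split. The primary analysis and the trial's success criteria are not affected.

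**What to change.** In SAP 10.11, define one observation window and use it for events, censoring and person-time. A workable choice is first infusion to the earliest of last study contact, end of adverse event collection in this study, or first PB-102-F60 infusion. Count only FCEs inside that window, censor event-free patients at its end, and use that time as the FCE rate denominator. Amend SAP 13.2, item 19, to match for the FCE curve.

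Optionally add an on-treatment version as a sensitivity analysis, with events and time both cut at the same stated point and a sentence on how deaths are handled. Keep on-drug exposure for the infusion-based tables.

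The cost is a few lines of SAP text and one derived date per patient before the final database lock. No new data and no protocol amendment are needed.
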